## Study Synopsis

Study Sponsor:	Henry Ford Hospital, Detroit, Michigan
Protocol Number:	1410401
Protocol Title:	Will Hydroxychloroquine Impede or Prevent COVID-19: WHIP COVID-19 Study
Indication:	This is a prospective, multi-site study designed to evaluate whether the use of hydroxychloroquine in healthcare workers (HCW), Nursing Home Workers (NHW), first responders (FR), and Detroit Department of Transportation bus drivers (DDOT) in SE, Michigan, can prevent the acquisition, symptoms and clinical COVID-19 infection.
Objective:	The primary objective of this study is to determine whether daily or weekly oral hydroxychloroquine (HCQ) therapy will prevent SARS-CoV-2 infection and COVID-19 disease in healthcare workers and first responders in SE, Michigan.
Study Design:	
The study will randomize a total of 3,000 HCW, NHW, FR and DDOT bus drivers within Henry Ford Hospital System, the Detroit COVID Consortium in Southeast, Michigan. The participants will be randomized in a 1:1:1 blinded comparison of daily HCQ, weekly HCQ, or placebo. A fourth non-randomized comparator group of HCW, NHW, DDOT bus drivers, and FR who are currently on standard HCQ therapy will be recruited to assess the impact of weight-based daily dosing of HCQ as compared to the randomized arms.
 
Eligible participants who are asymptomatic for pre-specified signs and symptoms suggestive of COVID-19 infection will have a whole blood specimen obtained at study entry.
 
Participants will be provided with weekly dosing of hydroxychloroquine (HCQ) 400mg po q weekly, daily dosing of HCQ 200mg po q daily following a loading dose of 400mg day 1, or placebo. Participants will receive monitoring at each study week visit to assess for the development of COVID-19 related symptoms, COVID-19 clinical disease, and medication side effects. At week 8 or if diagnosed positive, participants will provide additional samples of whole blood and complete the final study questionnaire.
 
Data including demographic, clinical results, work duties, location of main work area and possible exposures in the community will be collected through questionnaires and EMR review. Disease-specific, immunologic, and other serologic marker data will be obtained from stored samples.

Subject Population:	Approximately 3000 HCW, NHW, FR and DDOT bus drivers, age 18-75 years, presenting at participating clinical sites without symptoms of respiratory tract infection, as outlined in the Inclusion/Exclusion section of this protocol.

Duration of Subject Participation:	Each Participant's involvement in the study will last 8 weeks. Subject participation is required after consent for sample collection, questionnaires, and study calls and EMR review of clinical testing for respiratory infections.
Study Duration:	Up to 3 months for enrollment, 2 years for testing and publications, starting immediately following approval by the HFHS Institutional Review Board (IRB) and The United States Food and Drug Administration (FDA).

## Abbreviations/Definitions

AE;	Adverse Event
°C:	Degrees Centigrade (Celsius)
CAP:	Community Acquired Pneumonia
CFR:	Code of Federal Regulations
COVID-19:	SARS-CoV-2 clinical coronavirus disease which may be diagnosed by clinical and/or laboratory methods
CRL:	Case Report Log
DDOT	Detroit Department of Transportation
EMR:	Electronic medical record
FDA:	Food and Drug Administration
FR:	First Responders
HCW:	Healthcare Workers
ICF:	Informed Consent Form
ICH:	International Conference on Harmonization
IRB:	Nursing Home Workers
NHW:	Institutional Review Board
PI:	Principal Investigator
SAE:	Serious Adverse Event
SARS-CoVID -2:	Severe acute respiratory syndrome coronavirus 2 virus
SARS-CoVID-2 infection:	Detection of SARS-CoVID-2 infection by laboratory testing, can be symptomatic or asymptomatic presentation
SARS-CoVID-2 viremia:	Detection of SARS-CoVID-2 virus in blood, serum or plasma
SE:	South East

## 1 BACKGROUND

Community-acquired pneumonias (CAPs) can be due to viral or bacterial pathogens, and are one of the most common infectious diseases. Viral CAPs are most commonly caused by influenza A and B and other common cold viruses such as RSV, especially during winter months. Although their presentations can vary, only microbiological testing techniques can definitively identify the pathogen involved. In December 2019, a novel disease caused by a new virus now known as SARS-CoV-2, commonly referred to as COVID-19, was identified in Wuhan, China. Since then, the infection has spread worldwide, with over 663,828 cases identified and 30,822 deaths as of March 28, 2020 (Johns Hopkins Coronavirus Resource Center, <https://coronavirus.jhu.edu/map.html>). COVID-19 is a deadly pandemic which threatens the lives of millions of persons with mortality rates overall of 4.37%, but are highly very variable by region. For example, in Italy a crude mortality rate of 10.83% has been reported. In the United States, over 124,217 cases and 2,185 deaths have been reported, with the State of Michigan now representing the fourth most affected state, having 4,658 confirmed cases and 111 deaths reported (Johns Hopkins Coronavirus Resource Center, March 28, 2020; <https://coronavirus.jhu.edu/map.html>). HCW are at high risk of exposure given the close proximity in which they care for patients (Bureau of Labor Statistics, Occupational Employment Statistics) in addition to the growing shortages in personal protective equipment (PPE), which are paralleling the rise in COVID-19 cases (1,2). Recent COVID-19 outbreaks have demonstrated that up to 10-30% of HCW can become infected by the virus, and up to 85% may have asymptomatic/minimally symptomatic infection, promoting further spread of COVID-19 infection (2). Several epidemiological, societal and clinical interventions are currently ongoing to prevent the spread of COVID-19 disease, but to date, there are no published data on prevention strategies. This is a critical unmet need which must be addressed to preserve the population of active healthcare workers (HCW), nursing home workers (NHW), DDOT bus drivers, and first responders (FR) who are exposed to COVID-19 positive patients as part of their duties and represent the key component of our clinical response to this pandemic.

Chloroquine and hydroxychloroquine have demonstrated in-vitro efficacy in the treatment of COVID-19 (3). In 2005, Vincent *et al.* similarly demonstrated that chloroquine was effective in preventing the spread of SARS-CoV-2 in cell culture(4). Chloroquine interferes with the terminal glycosylation of the cellular receptor, angiotensin-converting enzyme 2, which is thought to impede the receptor binding and infection of the cell. Chloroquine was first discovered in 1934, and has been used for treatment of malaria since 1949 and other conditions such as systemic lupus erythematosus; and similarly, hydroxychloroquine (HCQ) has been used since 1955 (5,6).

These agents have a well-known safety profile. Multiple cohort studies have demonstrated the safety of HCQ in the lupus population, where it is routinely used even during pregnancy, with the only established contraindication for therapy being known retinopathy (7,8). Furthermore, the American College of Rheumatology does not recommend routine glucose-6-phosphate dehydrogenase screening, as clinical data have not demonstrated any significant risk of associated hemolysis in numerous cohort studies in both lupus and rheumatoid arthritis (8). Current dosing of HCQ for rheumatologic disease is weight-based, with the upper limit of dosing established at 5 mg/kg/day.

Malaria prophylaxis dosing of HCQ is given as 400mg po once a week for the duration of the exposure (5). Recent work by Gautret P *et al* demonstrated that doses of 600mg of hydroxychloroquine showed significant reduction of viral carriage at day 6 as compared to controls in patients with COVID-19 (9). Other investigators demonstrated in-vitro activity of HCQ against SARS-COV-2 with an EC50= 5.47 uM (10). Unfortunately, no data exists on the efficacy of these medications as prophylaxis in the prevention of COVID-19.

***The aim of this study is to demonstrate whether the use of hydroxychloroquine can prevent SARS-CoVID-2 infection and clinical COVID-19 disease in HCW, NHW, DDOT bus drivers and FR .*** Preventing COVID-19 transmission to HCW, FR, and DDOT bus drivers is a critical step in preserving the health care and first responder force, the prevention of COVID-19 transmission in health care facilities, with the potential to

preserve thousands of lives in addition to sustaining health care systems and civil services both nationally and globally. If efficacious, further studies on the use of hydroxychloroquine to prevent COVID-19 in the general population could be undertaken, with a potential impact on hundreds of thousands of lives.

## **2 STUDY OBJECTIVE**

The primary objective of this study will be to determine if the use of either daily or weekly hydroxychloroquine will lead to the prevention of SARS-CoV-2 infections and COVID-19 disease in HCW, NHW, DDOT bus drivers and FR in SE, Michigan.

### **2.1 Primary Aim**

1. To determine if the use of hydroxychloroquine as preventive therapy decreases the rate of acquisition of SARS-CoV 2 infections and clinical COVID-19 disease in Study Participants for each randomized treatment arm as compared to placebo.

### **2.2 Secondary Aims**

1. Compare the rates of SARS-CoV 2 infections between the randomized treatment arms and the control arms to determine the effect of HCQ dose in the prevention of COVID-19 viremia and disease.
2. Compare the rates of SARS-CoV 2 infections in the non-randomized comparator arm to the randomized groups to assess the impact of chronic weight-based dosing of HCQ for COVID-19 prevention.
3. To compare the rate of SARS-CoV 2 infections as measured by IgM/IgG in study participants receiving HCQ versus placebo.
4. To compare the seroprevalence of SARS-CoV 2 IgM/IgG positive samples at study

entry and study conclusion in all participants receiving HCQ compared to those receiving placebo.

5. To compare the development of clinical symptoms or COVID-19 diagnosis in participants presenting asymptotically at study entry but identified as seropositive by serology at entry between the randomized treatment arms and comparator arm.
6. To compare the clinical COVID-19 disease need for participants in each treatment arm to require emergency room visit, hospitalization or able to stay home without hospital care.
7. To determine the safety and tolerability of HCQ dosing for preventive strategy against COVID-19.
8. To examine other clinical determinants contributing to the risk of SARS-CoV 2 infection including demographics, work type and location, positive COVID-19 partners, possible exposures and clinical symptoms.
9. Examine the association between HCQ drug levels and development of COVID-19 symptoms or positive test results.
10. To identify immunologic, serological and inflammatory markers associated with acquisition and response to COVID-19 in both HCQ and placebo Participants developing laboratory or clinical confirmed disease.

### **2.3 Primary Endpoint**

1. Difference in new cases of COVID-19 disease between randomized treatment arms.

### **2.4 Secondary Endpoints**

1. The difference of SARS-CoV 2 infections between the randomized treatment arms and the control arms.

2. The difference of SARS-CoV 2 infections in the non-randomized comparator arm to the randomized groups.
3. The rate of SARS-CoV 2 infections as measured by IgM/IgG seroconversion in study participants receiving randomized HCQ versus placebo.
4. The seroprevalence of SARS-CoV 2 IgM/IgG positive samples at study entry and study conclusion in all participants receiving HCQ compared to those receiving placebo.
5. Emergence of clinical symptoms or COVID-19 diagnosis in participants presenting asymptotically at study entry but identified as seropositive by serology at entry between the randomized treatment arms and comparator arm.
6. To examine the level of care needed by participants in each arm developing COVID-19 as measured as requiring emergency room visit, hospitalization or able to stay home without hospital care.
7. The safety and tolerability of HCQ dosing for preventive strategy against COVID-19 as measured by adverse events and serious adverse events.

## **2.5 List of Outcomes**

1. Primary outcome: Clinical COVID-19 Disease with laboratory confirmation of infection
2. Secondary outcomes: SARS-CoV-2 infections, clinical COVID-19 disease without laboratory confirmation, serology (IgM and IgG) positivity, SARS-CoV-2 viremia, adverse events related to study medication or procedures, HCQ blood levels, immunologic and serologic markers associated with SARS-CoV-2 infection and COVID-19 and COVID-19 disease related ED visits and hospitalizations.

### **3. STUDY LOCATIONS**

This study will be conducted through at Henry Ford Health System, Detroit COVID Consortium and the Detroit Public Health building. The applicable Institutional Review Board (IRB) for each participating site will review and approve the study protocol and informed consent documents prior to any Participant enrollment. All HCW and NHW will be enrolled at one of the participating Henry Ford Health System (HFHS), Detroit COVID Consortium clinical sites. First responders and DDOT bus drivers will be enrolled at either the Detroit Public Health Building located at [name] or at participating HFHS sites. The total study duration is expected to be up to 2 years, with Participants enrollment targeted to begin immediately following IRB and FDA approval.

### **4. STUDY DESIGN**

The study will randomize a total of 3,000 HCW, FR, and DDOT bus drivers, age 18 to 75 years, through the Henry Ford Health System, Detroit COVID Consortium. HCW and NHW will include providers at both hospital/clinical settings and nursing homes. FR will include personnel working in both governmental, private or volunteer first responder services. DDOT bus drivers with the Detroit Department of Transportation. The participants who meeting study entry criteria and are not on HCQ prior to study enrollment will be randomized in a 1:1:1 blinded comparison of daily or weekly hydroxychloroquine versus placebo for 8 weeks.

A fourth non-randomized comparator group will be enrolled in the study comprising of HCW who are chronically on HCQ as part of their standard of care for their autoimmune disease(s). This will be an open enrollment group and will provide information of chronic weight-based daily therapy of HCQ effectiveness as a prophylactic/preventive strategy. These participants will continue on their therapy for the duration of the study.

The trial has implemented a pragmatic, adaptive enrichment design, where the efficacy analysis will be performed based on patients with negative screen for COVID-19 related symptoms at the baseline

and the safety analysis will be based on all randomized patients given there may be lag time to get any future COVID-19 test results back after the time of the study enrollment. The primary outcome of the study will be difference in development of COVID-19 disease between randomized arms. As new assays become available for research use for COVID-19 testing, these will be included in subsequent amendments if needed. The trial is also designed to have one interim look when a half of patients have completed the 8 weeks assessments for an early treatment efficacy, or a possible reassessment of study sample-size if the estimation of placebo rate is inadequate. A DSMB will be assembled to review interim analysis results. The DSMB Chair will also be provided a site SAE report weekly for safety review. Depending on response to the study intervention, the DSMB may decide it is necessary to stop/continue the trial if 1) there are safety concerns at any point in the trial or 2) there is evidence of treatment efficacy at the interim analysis; or recommendation for trial modification as it may be suggested, or 3) to continue the trial as designed. The primary aims of the DSMB are to decide if the study is safe to continue at the interim analysis timepoint and to monitor serious adverse events during the trial.

Participant eligibility will be assessed prior to study entry, and a screening questionnaire will be completed. Eligible asymptomatic participants will have study sample collections (whole blood) obtained at study entry. Clinical symptom data will be obtained at study screening and entry, to assess study eligibility focusing on the presence or absence of symptoms suggestive of COVID-19 infection.

The study's purpose and its potential risks and benefits will be explained to potential study Participants. Enrollment of study Participants will be done only after informed consent is obtained and a copy of the consent document is returned to the potential Participant. Consented Participants will be assigned a unique Subject ID that corresponds to the unique identifier assigned to the participant upon completion and submission of the online screening form.

In the event a Participant decides to withdraw consent before the baseline blood or study specimens can be collected, this Participant will be excluded from the study before they are randomized.

Participants will have 8 scheduled study encounters (see schedule of events, section 7.2).

Screening/baseline visit will include study screening, informed consent, and initial study questionnaires and specimen collections. At this visit, enrolled Participants will be provided with 8 weeks of hydroxychloroquine (HCQ) or placebo pills based on their randomized study group.

Participants will be asked to contact the study team if COVID-19 infection is established at any time during the study. For study weeks 1,2,3,5,6 &7, Participants will receive a monitoring questionnaire to assess for COVID-19 symptoms/diagnosis, adherence and medication side effects. These monitoring visits will be done by telephone and/or electronic encounters (virtual visits, email), whichever method the patient prefers to encourage adherence to the monitoring. Every effort will be made to obtain the weekly information from Participants and avoid missing timepoint information. Participants will have a +/- 3 day window to complete their scheduled study visits. As recommended in the FDA Guidance on Conduct of Clinical Trials of Medical Products during the COVID-19 Pandemic, updated on March 27, 2020, the approach of using electronic or virtual visits for study safety assessments will support study monitoring while increasing the safety for participants by reducing potential exposures to SARS-COV-2 while attempting to come to clinical areas for study visits, where no direct contact is needed as part of trial design.

The study Participant will have an in-house, face-to-face visit on week 4 of the study to obtain monitoring questionnaires to assess for COVID-19 symptoms/diagnosis, adherence and medication side effects, and collect study blood samples. At study week 8, participants will present for the final study visit and will provide additional samples of whole blood, as well as complete an end of study questionnaire. Participants who are determined to be positive for

COVID-19 by either study or clinical testing will complete the study at that timepoint. Every effort to obtain confirmatory test results for COVID-19 will be done, including patient self-report, at study evaluations if presenting with symptoms, and from supportive medical records or study testing. At this point, participants having been diagnosed with COVID-19 will be asked if they would be willing, within 30 days of recovery, to present for a study visit to provide a blood sample and answer an end of study questionnaire than can be scheduled at a later time. All participants will be monitored for safety 30 days post study completion.

Any potential study Participant who screens positive for COVID-19 symptoms or tests positive for SARS-CoV 2 during screening or subsequently during the trial, will be referred to their respective providers for further testing and care. HFHS employees will be directly referred to employee health for further evaluation.

Study questionnaires will obtain information on Participant demographics, clinical background, clinical symptoms, employment, work activities, location of main work area, known possible exposures to COVID-19 patients, potential medication side effects and adherence to study treatment regimens. Complete questionnaires are located in the appendix section.

Additional laboratory studies will include plasma serologies, cellular & systemic inflammatory markers as well as other disease associated markers. Samples will be stored for future studies as new markers of SARS-COV-2 infection and COVID-19 disease may be yet to be identified.

Samples will also be stored for potential future HCQ level testing. The testing will be done for samples from both randomized treatment arms and comparator arm subset of patients to assess their study compliance as compared to the medication adherence indicated in the study questionnaires. HCQ drug levels will provide further information regarding drug levels and their association with the effectiveness of the treatment strategies on prevention of symptom development and clinical & laboratory confirmed disease.

All collected specimens will be sent directly to the research laboratory for processing, analyses and storage. Patients who develop clinical symptoms for SARS-CoV-2 will have both clinical referral for testing and study blood collected. Additional testing for serology, immunology and other markers will be done later in the study. Samples will be stored in appropriately monitored – 80°C freezers or liquid nitrogen containers in the Division of Infectious Diseases and/or Translational and Clinical Research Center laboratories for testing.

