## 9 PARTICIPANT INVOLVEMENT ENDPOINT/FOLLOW-UP

All Participants who sign the Consent and Authorization Form and provide three (3) blood sample draws, complete the baseline and week 1- 8 assessments, or after acquiring COVID-19 infection at any point during the study period are considered to have completed participation in this study. Participants will be followed for 30 days after meeting study endpoint for safety purposes. No further follow-up by the study Investigator is planned for Participants involved in this study thereafter. Electronic medical records will be accessed to obtain information on any diagnostic testing done for COVID-19 as part of the Participants’ routine care which may lead to diagnosis of COVID infection, including but not limited to PCR, serologies, rapid diagnostic tests, and other related tests.

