## 10 SAFETY CONSIDERATIONS

### 10.1 Definitions of Adverse Events

An **Adverse Event (AE)** is any untoward medical occurrence in a Participant administered an investigational product or undergoing a procedure, which does not necessarily have a causal relationship with the treatment. An AE can be any unfavorable and unintended sign, symptom, or disease temporally associated with the use of an investigational product, whether or not it is related to the investigational product. *Development of COVID-19 disease will not be considered an adverse event as it is considered the study primary endpoint.*

A **Serious Adverse Events (SAE)** is any untoward medical occurrence that may present itself during a Subject's participation in a clinical trial that:

- Results in death,
- Is life-threatening,
- Requires inpatient hospitalization or prolongation of existing hospitalization,
- Results in persistent or significant disability/incapacity, or
- Is a congenital anomaly/birth defect.

Important medical events that may not result in death, be life threatening, or require hospitalization, may be considered a SAE when, based upon appropriate medical judgment, they may jeopardize the Participant and may require medical or surgical intervention to prevent one of the outcomes listed above. Medical care and hospitalization secondary to development of COVID-19 disease are considered study endpoints for this prevention study.

It should be noted that AEs that lead to hospitalization are considered SAEs. However, elective

hospital admissions not in response to an adverse event are not SAEs.

**Life-threatening** means that the Participant was, in the view of the PI, at immediate risk of death from the reaction as it occurred. This definition does not include a reaction that, had it occurred in a more serious form, might have caused death. Assessment of the cause of the event has no bearing on the assessment of the event's severity.

AEs will be considered to be **study-related** if the event follows a reasonable temporal sequence from a study-specific procedure and could readily have been produced by that study or medication procedure. Deaths, organ failures and other complications related to the Participants underlying conditions (including the disease or problem that caused the Participant to seek medical care), should **not** be considered study-related AEs.

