6.3 Study Aims, Hypothesis and Proposed Analysis

6.3.1 Primary Aim and Hypothesis

As noted below, the primary aim has been changed to: (based on Study Protocol dated 05/26/2020)

To determine if the use of hydroxychloroquine as preventive therapy decreases the rate of acquisition of SARS-CoV 2 infections [with clinical COVID-19 disease](#) in Study Participants [for each randomized treatment arm](#) as compared to placebo.

From: (based on original Study Protocol, dated at and after 04/06/2020)

To determine if the use of hydroxychloroquine as preventive therapy decreases the rate of acquisition of SARS-CoV 2 infections in Study Participants as compared to placebo.

Primary Hypothesis (P1): Hydroxychloroquine administered daily decreases the rate of acquisition of SARS-CoV 2 infections with clinical COVID-19 disease, compared to placebo; and hydroxychloroquine administered weekly decreases the rate of acquisition of SARS-CoV 2 infections with clinical COVID-19 disease, compared to placebo.

The **primary outcome** will be defined as clinical COVID-19 disease with laboratory confirmation of infection.

Presentation with COVID-19 symptoms during study follow-up (defined as fever $\geq 38^{\circ}$ C, or two or more non-fever symptoms that are new since the baseline) will refer participants to obtain SARS-CoV 2 testing through employee health or participants' primary care physician, with test results documented in their medical record.

Laboratory confirmation of SARS-CoV 2 infection (SARS-CoV 2 test positive) will be defined as at least one positive RT PCR, or both IgM and IgG positive serology. The lab test results can be obtained from (a) study blood samples (IgM and IgG serology), and (b) RT PCR test results ordered by a participant's primary care physician or through employee health.

All participants who test SARS-CoV 2 positive will be followed for at least 30 days after the first positive test for presentation of symptoms.

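### The SAP's primary outcome needs 30 days of symptom follow-up after a first positive test, but the protocol and its schedule of events do not provide for it

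*Protocol*

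**What the plan says.** **Outcome.** Protocol 2.5 gives "Primary outcome: Clinical COVID-19 Disease with laboratory confirmation of infection". SAP 6.3.1 supplies the parts. On the symptom side it names fever, or "two or more non-fever symptoms that are new since the baseline". Laboratory confirmation "will be defined as at least one positive RT PCR, or both IgM and IgG positive serology". SAP 6.3.1 then states that all who test positive "will be followed for at least 30 days after the first positive test for presentation of symptoms".

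**When participation ends.** Protocol 4 says that participants found positive for "COVID-19 by either study or clinical testing will complete the study at that timepoint". Protocol 9 lists those who finish all samples and assessments, "or after acquiring COVID-19 infection at any point during the study period are considered to have completed participation in this study".

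**Contacts after a positive test in the protocol.**
- Section 7.2: the column for withdrawal or a positive diagnosis holds a weekly assessment, a blood draw, the AE/SAE log and the Final Status form. No column follows it for a participant who has tested positive.
- Section 4: diagnosed participants are asked whether they are willing to attend a visit, timed from recovery, with a blood sample and an end-of-study questionnaire.
- Section 4.2: an unplanned visit 4 weeks after diagnosis, for final assessment and a blood draw.
- Section 9: "Participants will be followed for 30 days after meeting study endpoint for safety purposes". Section 4 has a similar 30-day safety sentence.

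**The concern.** With a two-part outcome, the order of the two parts matters. A participant whose symptoms come first is referred for testing and can meet both parts at the positive test. A participant whose positive test comes first is a primary event only if someone records symptoms that start later. The SAP relies on that record. The protocol, which is what sites work from, closes the participant at the point where it should begin.

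If the later symptoms are not recorded, a true primary event counts as a non-event. In S1 the same person moves from the symptomatic to the asymptomatic test-positive category. S6 is also involved, because its window can run to 30 days after a positive test, so it too needs contact or record review after that point. Missed events lower the rate in each arm, and the planned power has little to spare.

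**Working it through.** **Step 1. Does any protocol contact deliver the follow-up that SAP 6.3.1 assumes?**

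| Contact | Mandatory? | In the schedule (7.2)? | Stated to collect symptoms for the endpoint? |
|---|---|---|---|
| Assessment at the positive test (7.2) | attempted | yes | covers symptoms up to that day only |
| Post-recovery visit (4) | no, if willing | no | an end-of-study questionnaire; endpoint use not stated |
| Visit 4 weeks after diagnosis (4.2) | worded as planned for all diagnosed | no | not stated |
| 30-day follow-up (4, 9) | yes | no | no, for safety |

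No row meets all three conditions. The timings in sections 4 and 4.2 also differ: one counts from recovery, the other from diagnosis. Recovery has no clear meaning for a person without symptoms. On the safety contact, Protocol 10.1 says "Development of COVID-19 disease will not be considered an adverse event" and gives the reason that it is the primary endpoint. So an adverse-event log is not the place where later COVID-19 symptoms would be expected.

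**Step 2. Who is exposed?** In SAP 6.3.1, symptoms lead to testing, so most clinical tests should follow symptoms. Protocol 4 says further serology is run later in the study, and 7.3 says samples after entry are stored. A study serology result would therefore not usually end participation in real time. The exposed group is mainly people with a positive clinical test taken while asymptomatic.

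**Step 3. Reproduce the plan's power.** Inputs, from SAP 6.3.4.3, 6.4 and 6.7: 935 per arm; 10% on placebo and 6.8% in each HCQ arm; two-sided chi-square tests; step-up limits 0.05 then 0.0262 at the final look and 0.001 then 0.0005 at the half-way look. For each HCQ arm,

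z = (p̂₀ − p̂ₜ) / √[2·p̄(1 − p̄)/n], with p̄ the pooled rate.

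Both arms are declared effective if the larger p-value is below the first limit; otherwise the arm with the smaller p-value is declared effective if it is below the second. Power is the chance of declaring at least one arm. With 400,000 simulated trials the result is 0.78, against 0.800 in SAP Table 1. At 900 per arm it is 0.763 against 0.770. With rates of 7.3% and 6.3% it is 0.800 against 0.800 (n=900) and 0.815 against 0.811 (n=935). Agreement is within two points, so losses are measured from the computed 78%.

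**Step 4. Illustrate a loss.** Assume a share f of true primary events tests positive before symptoms, that all of these are missed, and that f is the same in every arm. Each rate becomes rate × (1 − f). Expected events are 935 × that rate.

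| f (assumed) | Placebo rate | HCQ rate | Expected events, placebo vs each HCQ arm | Power |
|---|---|---|---|---|
| 0 | 10.0% | 6.80% | 93.5 vs 63.6 | 78% |
| 5% | 9.5% | 6.46% | 88.8 vs 60.4 | 76% |
| 10% | 9.0% | 6.12% | 84.2 vs 57.2 | 73% |
| 20% | 8.0% | 5.44% | 74.8 vs 50.9 | 68% |

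The relative reduction stays at 32% in every row, because both rates shrink by the same factor. Under this assumption the cost is power, not bias in the relative effect.

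**The case against.** The strongest reply is that the plan already covers this. SAP 6.3.1 states the 30-day symptom follow-up under the primary outcome, and S6 has its own 30-day window. The protocol does not end contact at the positive test: there is a visit 4 weeks after diagnosis, which could record symptoms that began after the test, and a post-recovery visit with a questionnaire. Protocol 4 says study questionnaires ask about clinical symptoms. SAP Appendix A lists COVID Status and Final COVID_Status forms, added on 7/9/2020 to capture COVID events. Protocol 10.1 keeps COVID-19 out of adverse events because it is the endpoint, and treats COVID-19 hospital care as an endpoint too. Finally, the SAP cites a protocol dated 05/26/2020 and covers Michigan and Ohio, while the supplied protocol covers SE Michigan, so part of the mismatch may be version lag.

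Most of this stands, and it limits the consequence. A reader might infer that pre-symptomatic positives would be missed as primary events, or that S6 events are lost. The documents support neither. They show routes by which these events could be recorded, and they do not show the fields of the COVID event forms, so one cannot say that symptoms are left out.

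What the reply does not remove is the gap in instruction. One visit is voluntary, the other is absent from the schedule and silent on symptoms, and the follow-up the SAP relies on is described in the protocol as safety contact. The COVID event forms came after recruitment had begun on April 10th, and nothing says that they cover 30 days after a positive test.

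**Conclusion.** The finding is a mismatch between protocol and SAP on how the primary outcome is ascertained. The SAP depends on at least 30 days of symptom follow-up after a first positive test; Protocol 4, 4.2, 7.2 and 9 do not put it into practice. If sites follow the protocol wording alone, some participants with a positive clinical test before symptoms could be misclassified as asymptomatic infections in the primary and S1 analyses.

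The size is unknown. The documents give no share of cases that test positive before symptoms. The Background figure of up to 85% with asymptomatic or minimal infection does not supply one, since it says nothing about the order of test and symptoms. If the SAP follow-up is carried out, the loss is near zero and the planned power is unchanged. The 76%, 73% and 68% figures rest on assumed shares of 5%, 10% and 20%, on every such case being missed, and on equal loss in all arms. It is tempting to quote a larger fall, such as 61% at a 30% share, as the expected effect. Nothing in the documents supports that.

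**What to change.** Reconcile Protocol 4, 4.2, 7.2 and 9 with SAP 6.3.1:
- Add to the schedule of events a symptom and ED/hospitalization assessment covering the 30 days after the first positive test. The existing virtual contacts and the 4-week visit could carry it; the SAP sets no frequency, so weekly contact is one option, not a requirement.
- State that these data are efficacy data for the primary outcome, S1 and S6, and name the form that holds them. If the COVID event forms already do this, say so.
- Reconcile the timing of the post-diagnosis visits in sections 4 and 4.2.
- Complete the Final Status form only after the 30-day window.
- State which protocol version the SAP governs.

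The cost is protocol wording and a few extra virtual contacts per positive participant.
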